7.2.3.1 SCREENING

- Obtain informed consent of potential participant verified by signature on written informed consent form
- Review medical history, including biomarker status and cancer diagnosis, to determine eligibility based on inclusion/exclusion criteria (**Sections 5.1-5.2**)

The information contained in this protocol and all other information relevant to this study are confidential and proprietary information of Strata Oncology Inc., except as may be required by federal, state or local laws or regulation, and may not be disclosed to others without prior written permission of Strata.

Page 36 of 56

- Enter data from any standard of care procedures in the EDC, including ECOG status
- Submit biomarker confirmation form through the EDC
- If no historical CGP test results are available, submit an FFPE tumor specimen for confirmation by a central lab.

7.2.3.2 BASELINE

- Verify eligibility per inclusion/exclusion criteria
- Review of medications
- Negative pregnancy test (urine or serum)
- Obtain two 10 mL tubes of whole blood and complete research blood collection form
- Dispense study drug and review dosing instructions
- Administer study drug and/or review administration instructions with participant
- Perform drug accountability
- Enter data from any standard of care procedures in the EDC, including ECOG status
- Document any AEs or SAEs

7.2.3.3 ON TREATMENT

- Review of medications
- Negative pregnancy test (urine or serum)
- Obtain two 10 mL tubes of whole blood and complete research blood collection form every 8 weeks during the first year of treatment and every 12 weeks thereafter and once upon disease progression
 - Complete research blood collection form
- Dispense study drug
- Administer study drug and/or review administration instructions with participant
- Perform drug accountability
- Enter data from any standard of care procedures in the EDC, including ECOG status
- Document any AEs or SAEs

7.2.3.4 POST-TREATMENT

Study drug will be discontinued upon disease progression or based on physician's discretion as described in **Section 5.5**. Site staff should collect unused study drug and any empty packaging and perform drug accountability upon study drug discontinuation. Participants that discontinue drug will remain on study for 3 years from the date of informed consent for follow-up data entry purposes only. No additional study specific procedures will occur following discontinuation. Participants will continue to see their physician for SOC clinic visits. Site staff will be responsible

The information contained in this protocol and all other information relevant to this study are confidential and proprietary information of Strata Oncology Inc., except as may be required by federal, state or local laws or regulation, and may not be disclosed to others without prior written permission of Strata.

Page 37 of 56

for collecting and entering the information below in EDC from the participants SOC clinic visits every 3 months.

- Medical history (specifically, disease recurrence and/or survival status)
- Concomitant medications (specifically, anticancer therapies)
- Standard of care procedures, including ECOG status

7.3 EFFICACY ASSESSMENTS

7.3.1 tdMETA COHORTS

Study procedures and evaluations to assess efficacy are listed below.

Response Assessment:

Participants will undergo tumor assessments as designated in the Schedule of Activities (**Table C, Section 7.2.1**) until disease progression (regardless of whether or not the participant is still receiving study treatment) or until the participant discontinues the study drug or starts alternative anticancer treatment. At the investigator's discretion, tumor assessments may be repeated at any time if progressive disease is suspected.

Confirmation assessment of progressive disease must be obtained at least 4 weeks after the initial disease assessment indicating progressive disease. After confirmation of progressive disease, participants must complete the end of treatment visit and enter the post-treatment follow-up period.

All active study participants who discontinue study drug for reasons other than disease progression (e.g., AEs) will continue tumor assessments until death, disease progression, initiation of another systemic anticancer therapy, lost to follow-up, withdrawal of consent, PI's decision, or study termination, whichever occurs first.

Measurable and evaluable lesions should be assessed and documented at baseline. Response assessments performed as standard of care prior to obtaining informed consent and within 28 days prior to enrollment do not have to be repeated at screening.

Baseline disease assessments will include a CT scan of the chest and abdomen/pelvis. CT scans of the neck and/or extremities should be performed as clinically indicated. Post-baseline disease assessments will include a CT scan of the chest and abdomen/pelvis for all participants. CT scans of the neck and/or extremities and brain MRIs should be repeated throughout the study if there is evidence of disease at screening or if clinically indicated. All scans should be performed in accordance with RECIST 1.1 and with contrast. If contrast is

The information contained in this protocol and all other information relevant to this study are confidential and proprietary information of Strata Oncology Inc., except as may be required by federal, state or local laws or regulation, and may not be disclosed to others without prior written permission of Strata.

Page 38 of 56

contraindicated (i.e., in participants with known contrast dye allergy or impaired renal clearance), a chest CT without contrast and an abdomen/pelvis MRI without contrast may be performed.

If a CT scan for a tumor assessment is performed in a positron emission tomography/CT scanner, the CT acquisition must be consistent with the standards for a full contrast diagnostic CT scan.

Images will be collected and centrally stored to allow for retrospective review, if indicated.

All measurable and evaluable lesions should be reassessed at each subsequent tumor evaluation. The same radiographic procedures used to assess disease sites at screening should be used for subsequent tumor assessments (e.g., same modality and contrast protocol).

Response will be assessed by the Investigator using RECIST 1.1 (primary; see operations manual) and iRECIST (secondary; see operations manual). Assessments should be performed by the same evaluator, if possible, to ensure internal consistency across visits. Results must be reviewed by the investigator before dosing at the next cycle.

7.3.2 μMETA COHORTS

Post-SOC imaging or testing, investigators should denote disease-free status within the electronic health record (EHR). The physician note should also be entered into the EDC.

Please review the study's operations manual for specific instructions.

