4 STUDY DESIGN

4.1 OVERALL DESIGN

Participants who are 18 years of age or older, have been diagnosed with histologically documented solid tumors, have an eligible biomarker profile, and are planned for treatment may be eligible for this study according to the criteria in **Sections 5.1-5.2** and the supplemental criteria in the specific biomarker/drug cohort appendix.

Each biomarker/drug cohort will be described in an appendix to this study protocol. Appendix information includes investigational product overview, rationale for biomarker/drug combination, additional cohort-specific eligibility criteria, study treatment including dosing and administration guidelines, along with known adverse reactions.

After obtaining informed consent, study staff shall assess individual participant eligibility using the criteria in **Sections 5.1-5.2** and the supplemental criteria in the specific appendix they are targeting for enrollment. The designated study staff will enter the participant's details into the electronic data capture (EDC) to support a sponsor-required confirmation of biomarker eligibility. Upon confirmation of eligibility and informed consent procedures, the participant will be formally enrolled into the study. Participants will be treated with the applicable cohort's study drug according to dosing instructions in the approved product labeling or provided Investigator's Brochure (IB).

For participants who exhibit more than 1 eligible biomarker result, the treating physician should determine the most appropriate cohort assignment. Factors for consideration include the drug's dosing and administration guidelines, as well as the commercially available product prescribing instructions or provided IB.

A leftover tumor specimen (if historical comprehensive genomic profiling (CGP) and/or ribonucleic acid (RNA) profiling results are not available for submission) and blood sample for ctDNA analysis will be collected at study entry (prior to therapy start). Blood samples will be

The information contained in this protocol and all other information relevant to this study are confidential and proprietary information of Strata Oncology Inc., except as may be required by federal, state or local laws or regulation, and may not be disclosed to others without prior written permission of Strata.

Page 23 of 56

collected and CT/MRI scans will be performed until treatment discontinuation as outlined in the Study Schedule of Activities (SOA) (**Section 7.2**).

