7.2.1 SCHEDULE OF ACTIVITIES

The schedules of activities (SOA) for both the tdMeta and μMeta cohorts are detailed in **Table C** and **Table D**. StrataPATH is designed to mimic real-world practice and will have a limited number of study-specific visits (**Section 7.1**). The visit schedules are comprised of a combination of study-specific visits and standard of care (SOC) visits. Participants will be followed for up to 3 years from the time of consent.

SOC procedures listed in the SOA typically occur during standard clinical visits and are to be documented within the EDC system at the timepoints outlined in the SOA.

The information contained in this protocol and all other information relevant to this study are confidential and proprietary information of Strata Oncology Inc., except as may be required by federal, state or local laws or regulation, and may not be disclosed to others without prior written permission of Strata.

Page 32 of 56

Table C: StrataPATH Schedule of Activities – tdMeta Cohorts

SCHEDULE OF ACTIVITIES STR-004-001: StrataPATH tdMeta Cohorts	STUDY VISITS (participation up to 3 years)			
	Screening	Baseline	On Treatment	Post-Treatment ^g
Study Procedures				
Review and Sign Informed Consent Form	X			
Eligibility Criteria Review (Main and Cohort-Specific)	X	X		
Biomarker Confirmation	X			
CT Scan or MRI of Abdomen, Chest, and Pelvic Area		X ^a	X ^{b,c}	
RECIST 1.1 (or iRECIST) Assessment		X	X ^{b,c}	
Blood Draw: Whole Blood		X	X ^{b,c}	
FFPE Tissue Collection	X ^d			
Study Drug Administration		X ⁱ	X ⁱ	
Study Drug Accountability		X	X	X ^h
Study Drug Discontinuation				X ^h
Standard of Care (SOC) Procedures^e				
Documentation of Biomarker Results	X ^e			
Demographics	X ^e			
Medical History	X ^{e,f}		X ^e	X ^e
Cancer Diagnosis	X ^e			
Prior and Concomitant Medications	X ^{e,f}		X ^e	X ^e
Physical Exam (Complete or Abbreviated)	X ^e		X ^e	X ^e
ECOG Performance Status	X ^e	X ^e	X ^e	X ^e
Height, Weight, Vital Signs	X ^e		X ^e	X ^e
Electrocardiogram (EKG)	X ^j		X ^e	X ^e
Echocardiogram (Echo)	X ^j			
Hematology	X ^e		X ^e	X ^e
Serum Chemistry	X ^e		X ^e	X ^e
Urine Pregnancy Test, Serum Pregnancy Test ^k	X ^e	X ^e	X ^e	
Safety Evaluation				
Adverse Events/Serious Adverse Events		X	X	X

^aIf a scan was performed within 28 days of the baseline visit, these results should be submitted to the study.

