^bCollect every 8 weeks (± 2 weeks) during year 1 on treatment. After year 1 of treatment, collect every 12 weeks (± 2 weeks). Collect upon disease progression.

^cConfirmation of progression (e.g., confirmatory scan 4 weeks after initial progression assessment).

^dOnly required if historical comprehensive genomic or Strata RNA profiling results are not available or otherwise indicated within the cohort-specific criteria. Site should collect and submit a leftover tumor tissue specimen to the Strata Lab for confirmatory testing with a central next generation sequencing test.

^eThe specified SOC procedures should be conducted only if they are necessary for clinical care and should not be done for research purposes only. If any of these SOC activities are conducted at a regular clinic visit, the data obtained must be entered in the EDC for the study.

^fEnter information from medical records obtained up to 30 days prior to the screening visit.

^gEvery 3 months for up to 3 years from the date of consent or until death, whichever comes first.

^hStudy drug will be discontinued upon progression or per physician discretion. Study drug discontinuation and accountability activities will only be performed once during post-treatment.

ⁱThe frequency of study drug dispensing and administration will be determined by the biomarker/study drug cohort in which the patient is enrolled.

^jIf not SOC and historical data not available, can be research activity.

^kOnly if urine test is positive or inconclusive; serum test can be research activity.

The information contained in this protocol and all other information relevant to this study are confidential and proprietary information of Strata Oncology Inc., except as may be required by federal, state or local laws or regulation, and may not be disclosed to others without prior written permission of Strata.

Page 33 of 56

Table D: StrataPATH Schedule of Activities – μMeta Cohorts

SCHEDULE OF ACTIVITIES μMeta Cohorts STR-004-001 - StrataPATH	STUDY VISITS (participation up to 3 years)			
	Screening	Baseline	On Treatment	Post-Treatment ^e
Study Procedures				
Review and Sign Informed Consent Form	X			
Eligibility Criteria Review (Main and Cohort-Specific)	X	X		
Biomarker Confirmation	X			
Blood Draw: Whole Blood		X	X ^b	
FFPE Tissue Collection	X ^a			
Study Drug Administration		X ^g	X ^g	
Study Drug Accountability		X	X	X ^f
Study Drug Discontinuation				X ^f
Standard of Care (SOC) Procedures				

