7.2.2.4 POST-TREATMENT

Study drug will be discontinued upon disease progression or based on physician's discretion as described in **Section 5.5**. Site staff should collect unused study drug and any empty packaging and perform drug accountability upon study drug discontinuation. Participants that discontinue drug will remain on study for 3 years from the date of informed consent for follow-up data entry purposes only. No additional study specific procedures will occur following discontinuation. Participants will continue to see their physician for SOC clinic visits. Site staff will be responsible for collecting and entering the information below in EDC from the participants SOC clinic visits every 3 months.

- Medical history (specifically, disease recurrence and/or survival status)
- Concomitant medications (specifically, anticancer therapies)
- Standard of care procedures, including ECOG status

7.2.3 μMETA COHORTS

Note that μMeta cohorts will not have CT/MRI scans or RECIST 1.1 (or iRECIST) assessments performed.

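### tdMeta participants who stop drug without progression: the protocol both continues and ends their tumour assessments, which leaves DoR, and possibly ORR, dependent on which text a site follows

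*Protocol*

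**What the plan says.** The question is what happens to scans and RECIST reads when a tdMeta participant stops drug for toxicity, or at the physician's discretion, without progression.

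**Text that continues them.** Section 7.3.1, third paragraph, says active participants "who discontinue study drug for reasons other than disease progression (e.g., AEs) will continue tumor assessments until death" or one of six other events, whichever is first: progression, another systemic anticancer therapy, loss to follow-up, withdrawal of consent, the PI's decision, or study termination.

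**Text that ends them.**
- Section 4.1: samples are "collected and CT/MRI scans will be performed until treatment discontinuation as outlined in the Study Schedule of Activities".
- Section 7.2.2.4 covers this group, since it opens "Study drug will be discontinued upon disease progression or based on physician's discretion as described in" another section. It then says "Participants that discontinue drug will remain on study for 3 years from the date of informed consent for follow-up data entry purposes only" and "No additional study specific procedures will occur following discontinuation". Section 7.1.1 lists CT/MRI scans and RECIST assessments among the study-specific procedures.
- Table C marks the row "CT Scan or MRI of Abdomen, Chest, and Pelvic Area" and the RECIST row at Baseline and On Treatment only. Footnote b gives the interval as every 8 weeks "during year 1 on treatment. After year 1 of treatment, collect every 12 weeks", so no interval is defined off drug.

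**Text that points both ways.** The first sentence of 7.3.1 runs assessments to progression, "regardless of whether or not the participant is still receiving study treatment) or until the participant discontinues the study drug". Section 6.4 says stopping drug is not leaving the study and that remaining procedures are completed on or off treatment, but only as the protocol indicates, which leads back to the conflicting sections.

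**The concern.** ORR (primary) and DoR (secondary) rest on investigator-recorded RECIST 1.1 assessments (Section 9.3.2), and DoR ends at the first documented progression (Table A). The rule on scan duration therefore decides which off-drug responses and progressions can enter the data.

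Under the stop text, a responder who stops for toxicity has no scheduled assessment after that date. DoR is then cut off at drug stop, for a reason that may be related to later progression. A response first visible after drug stop may never be recorded. With 25-30 sites, both practices could occur within one 35-patient cohort. A SAP can set a censoring rule, but it cannot supply a RECIST read that was never scheduled, so the protocol has to settle this.

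**Working it through.** **Text check.** Take one participant who stops drug for an AE at week 20 without progression, where the PI makes no decision to end assessments. Section 7.3.1, third paragraph: the next scan is due. Section 4.1: scans have ended. Section 7.2.2.4 with 7.1.1: the scan is not to occur. Table C: no mark and no interval. First sentence of 7.3.1: either answer. Section 6.4: refers back to the protocol. No order of precedence is stated.

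**The plan's own figure.** Inputs from Section 9.1: 12 patients in stage 1, stop at 1 or fewer responses, 35 in total, reject at 6 or more, null rate 0.05, target rate 0.30. Exact two-stage binomial:

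P(reject | p) = Σ over x = 2..12 of Bin(x; 12, p) × P(Bin(23, p) ≥ 6 − x)

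This gives 0.0052 at p = 0.05 and 0.901 at p = 0.30. The stated pair (0.001 and 88%) is not reproduced; rejection at 7 or more gives 0.0012 and 0.875. That is a separate matter. The baseline below is the written rule.

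**ORR sensitivity.** Let q be the share of responses first documented only off drug. The documents give no value, so q is an assumption. Under the stop text the recorded rate is 0.30 × (1 − q).

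| q | recorded rate | stage-1 pass | power |
|---|---|---|---|
| 0 | 0.3000 | 91.5% | 90.1% |
| 2.5% | 0.2925 | 90.6% | 89.0% |
| 5% | 0.2850 | 89.7% | 87.7% |
| 10% | 0.2700 | 87.5% | 84.6% |

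**Stage-1 boundary.** P(exactly 2 of 12) at 0.30 is 0.168. Harm also needs at least one of those two responses to be off-drug only. At q = 5% this is 0.168 × (1 − 0.95²) = 0.168 × 0.0975 = 0.016, or 1.6%. Most of the 1.8-point fall in the table (91.5 − 89.7) comes from here.

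**DoR sensitivity.** Expected responders at 0.30: 0.30 × 35 = 10.5 per cohort. Assume a share f stops without progression. Section 2.3 reports AE discontinuation of 9% (advanced disease) and 14% (adjuvant) for one drug; 25% is a high case. Responders affected: 10.5 × 0.09 = 0.9, 10.5 × 0.14 = 1.5, 10.5 × 0.25 = 2.6.

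Assume a 9-month median on drug, so λ = ln 2 / 9; a stopping hazard μ = λf/(1 − f); and an off-drug progression hazard hλ. If Kaplan-Meier censors at drug stop, the median is 9.0 months. With continued scans the median t solves

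exp(−(λ+μ)t) + μ[exp(−hλt) − exp(−(λ+μ)t)] / (λ + μ − hλ) = 0.5

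- h = 2: 8.8 (f = 9%), 8.6 (14%), 8.3 (25%) months.
- h = 0.5, f = 25%: 9.6 months.
- h = 1: 9.0 months, no change.

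**The case against.** The strongest reply is that a site could resolve the conflict sensibly. The third paragraph of 7.3.1 is the only text that names this exact group, the other sections are general, and 6.4 leans towards continuing. This has weight, but the protocol does not say that the specific text governs, and the first sentence of the same section contains the opposite rule.

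A reader might infer that the two orders can never both be obeyed. The documents do not support that. The PI's decision is one of the listed end events, so a PI who ends scans at drug stop complies with every section. That removes the logical impossibility but leaves the choice to each site. Nor can one say that the first sentence of 7.3.1 simply ends assessments at drug stop, since its parenthesis says the reverse.

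A reader might also infer that off-drug disease data are wholly lost. They are not. Section 7.2.2.4 collects recurrence status and standard-of-care procedures every 3 months, 7.1.2 requires such data to be entered, and 4.1 allows imaging to be requested once an efficacy signal appears. What is missing is scheduled RECIST assessment, which ORR and DoR use.

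Finally, 16.8% (P of exactly 2 of 12 at a true rate of 0.30; 28.3% at 0.20) might be taken as the risk to a cohort. It is only the chance of sitting on the boundary. Table E's mITT requires a post-baseline scan, but the protocol does not assign ORR to that population, so no effect on the denominator can be claimed.

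**Conclusion.** The contradiction stands in the current text and should be corrected. It is confined to tdMeta participants who stop drug without progression. Its main consequence is for DoR, where responders who stop for toxicity may or may not have scheduled follow-up to the event; the effect on ORR is possible but less likely.

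The size is unknown from the documents and probably small. At an assumed q of 5%, stage-1 pass falls by about 2 points and power of the written rule by 2.4 points (90.1 − 87.7); at q = 0 nothing is lost. Median DoR moves by 0.2 to 0.4 months if 9-14% stop and the off-drug hazard doubles, by up to 0.7 at 25%, and not at all if the hazard is unchanged. These figures rest on an assumed q, an assumed 9-month median, exponential times and an assumed stopping share. The 9% and 14% are for all treated patients on one drug rather than responders, and the 14% comes from an adjuvant setting.

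**What to change.** Adopt the third paragraph of 7.3.1 throughout, because DoR ends only at documented progression.

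1. **7.3.1, first sentence:** remove discontinuation of study drug as an end of assessments. Keep the start of alternative anticancer treatment as an end event.
2. **7.2.2.4:** after the ban on study-specific procedures, add an exception for the CT/MRI and RECIST assessments that 7.3.1 requires. These are the continued assessments after a stop without progression and the confirmatory assessment of progression. Exempting only non-progressors would strengthen the ban against the confirmatory scan due at least 4 weeks after progression.
3. **Table C:** mark CT/MRI and RECIST in the Post-Treatment column for these cases. Keep the 8-week then 12-week interval, counted from first dose for these two rows.
4. **4.1:** for CT/MRI, end scans at an event listed in Section 7.3.1 instead of at treatment discontinuation. A reference is safer than a shorter list of end events, which would create a new mismatch.

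Cost: four text edits in the next amendment. Scans continue for the few participants who stop without progression. At the assumed 9-14% that is 0.09 × 35 = 3.2 to 0.14 × 35 = 4.9 per cohort, with at most 52/8 = 6.5 scans each in a first year. The third paragraph of 7.3.1 already requires them.
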